## [Outcomes and Instruments](#)

### [Primary research outcomes](#)

- Pain-related fear avoidance (FACS): The Fear-Avoidance Components Scale (FACS) was developed, which incorporates important components of previous FA-related measures, and includes components of the FA model not previously considered in the earlier-developed questionnaires, within a framework of the most current FA model of Vlaeyen (44,45). The FACS has demonstrated acceptable test/retest reliability ( $r = .90\text{--}.94$ ) and internal consistency (Cronbach  $\alpha=.92$ ) (46).

Pain-related fear avoidance (FA), a common problem for patients with painful medical conditions, involves pain-related catastrophizing cognitions, hypervigilance, and avoidance behaviors, which can ultimately lead to decreased functioning, depression, and disability (47).

- Pain intensity: (Visual Analogue Scale VAS): The VAS has been used in previous studies investigating changes in pain and, specifically, in all the randomized trials of interventions for back pain in pregnancy included in or published since the Cochrane and systematic reviews (42). The visual analog scale (VAS) was used for assessment of pain before and after the intervention. Measurement will be performed with a 10-cm scale marked with 1-cm increments. Pain felt by participants will be recorded. Pain was rated on a scale of 0 a 10, with 10

representing the most excruciating pain. The value indicated on the scale by the participants was used as the score. Previous studies have shown that the reliability of the VAS ( $r=0.76-0.84$ ) is high (46).

- Disability and Physical function: In this paper, we focus on the 2 back-specific measures of function recommended in the “core-set,” the Roland-Morris disability Questionnaire (RMDQ) and the Oswestry Disability Index (ODI). They are the most commonly used measures of function in back pain research (46).

The RMDQ will be used for measurement of the severity of disability in participants who had less severe LBP. There are 24 categories comprised of yes or no questions. Each participant can have a maximum score of 24. Scoring closer to 24 indicates greater functional disability (48,49). Quoted test-retest correlations include 0.91 (same day), 0.88 (1 week), and 0.83 (3 weeks) (48).

The Oswestry low-back pain disability index (ODI) will be completed by the participants and included 10 questions assessing activities of daily living in order to examine the functional level when experiencing LBP. Each category will be scored from zero to five with regard to the severity of disability caused during daily life. The intraclass correlation coefficient was  $r=0.938$ , and the Cronbach’s alpha was 0.918 (day 1) and 0.895 (day 7) in the validation (44,45).

#### Secondary research outcomes

- Satisfaction with Virtual Reality intervention

To assess the Satisfaction with the Virtual Rehabilitation Systems we will use the USEQ (User Satisfaction Evaluation Questionnaire). The USEQ is a questionnaire that is designed to properly evaluate the satisfaction of the user (which constitutes part of usability) in virtual rehabilitation systems. The USEQ is a reliable questionnaire with adequate internal consistency, Cronbach alpha coefficient was 0.716, and patients found the USEQ to be an easy-to-understand questionnaire with a convenient number of questions (50).

Primary and Secondary Outcomes	Definition	Type
Pain related fear avoidance	FACS	Self-reported
Pain intensity	VAS	Registered / Self-reported
Disability and physical function	RMDQ, ODI	Registered / self-reported
Satisfaction and usability	USEQ	Self-reported

Table 2. Primary and Secondary Outcomes

#### Data collection, monitoring, and management

Once participants have been informed and agree to participate in the study, data will be collected for statistical analysis. This data collection will take place in the period September-December 2022. Initial assessment (Pre) and final 4-week assessment (Post) will be carried out by the research team including, rehabilitation and physiotherapy department. The data will be aggregated to research database created for this purpose and managed by the principal's researches using exportable data tables for statistical analysis.

The research is designed in 4 stages as presented at Figure 1 study design flow diagram:

Stage 1 includes 2 different processes: firstly the identification of candidates, the provision of prior information and the signing of informed consent if subjects agree to participate. Secondly, the assessments by the physiotherapy department. The initial assessment includes a self-made clinical interview for anamnesis with self-administered questionnaires, which will be completed including FACS, RMDQ, ODI and VAS (T0-Pre). This stage ends with the referral to the physiotherapy intervention team.

Stage 2 includes: Design of a personalised physiotherapy programme (CG and EG) according with Physiotherapy department plus VRi intervention in the (EG).

Stage 3 includes: 4 weeks physiotherapy intervention plus VRi program with the supervision of the physiotherapy department. Initials 1 to 1 session is offered with technology management and patient education. Daily follow up sessions include the progression and adverse events records. Physiotherapy team will update programmes according to participant's feedback.

Stage 4 includes: Final assessments and evaluation (T1-Post). At this stage Physiotherapy team and principals researches compile the results of outcomes after 4 weeks including FACS, RMDQ, ODI, VAS and USEQ. Satisfaction questionnaire will be added to research data's for statistical analysis.

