## Objectives

The main objective of this research is to evaluate the effectiveness of a combined VR and Physiotherapy 4-weeks program compared to a standard physiotherapy intervention in LBP and PP pregnancy woman's to improve pain-related fear avoidance, pain intensity, disability and functional level.

The secondary aim is to investigate patient satisfaction with the VR intervention.

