## Control Group (CG)

Following clinical practice guidelines, subjects in the control group will receive multidisciplinary rehabilitation programmes with coordinated delivery of supervised exercise therapy, cognitive behavioural therapy (education on pain), as well as therapeutic massage to relieve low back pain during pregnancy.

Typical physiotherapy session:

- Control of daily health
- Analgesic and muscle-relaxing (thermotherapy, tens, therapeutic massage)
- Exercise session:
  - o Initial warm-up: 5–10 min (thoracic, lumbar and pelvic joint mobility exercises adapted to the pregnancy progress).
  - o Strengthening and flexibility exercises (thoracic, lumbar and pelvic joint exercises adapted to the pregnancy progress).
  - o Return to calm: 5 min breath and stretching exercises
  - o Recording of incidents and patient/physiotherapist feedback

Experimental Group (EG). VR intervention:

- o Subjects in the experimental group will receive the same treatment described for the control group
- o Subjects in the experimental group will receive an additional VR intervention.

The immersive virtual reality (VRi) system is composed by a head mounted display (Oculus Quest, Facebook Inc.) and two controllers. Oculus Quest headset is a wireless and portable Android-based device which supports positional tracking with six degrees of freedom (360°). The internal cameras allow to show an external signal with the user view, which helps to monitoring the patient execution. A Wi-Fi connection and a training area of 2x2 meters are needed.

At the end of each session, participants will experience an immersive virtual landscape displayed by Nature Trek VR software (<https://naturetreksvr.com/>). First, participants will be placed in a sit down position and guided for their breathing control during 5 minutes (“meditation Lotus option”). After that, they will be encouraged to freely move around a relaxing virtual environment during 15 minutes taking special attention to soothing sounds of nature. The themed environment will be selected based on the preferences of the participants.

At the beginning of the study, advice is given on general care, in physical activity and issues concerning drug intake. Patients are advised to refrain from any other specific training during the intervention period. Any deviations from the adherence and practice of the VRi are recorded daily, noting any adverse incidents.

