#### Discussion:

Evidence from single studies suggests that some therapy modalities or a multi-modal intervention (manual therapy, exercise and education) improves pelvic pain and pregnancy related outcomes. However, the current scientific evidence leaves many issues unresolved like type and intensity of exercise and physiotherapy intervention effectiveness for different outcomes. Since evidence showing that one form of exercise is better than another is not available, guidelines recommend exercise programmes that take individual needs, preferences, and capabilities into account in deciding about the type of exercise. This lack of standardized exercise programmes may lead to significant intervention biases in the different studies and consequently the low or moderate level of evidence.

Due to the high prevalence, the recurrence, the interference on daily activities, work capacity and sick leaves, and the increased psychological stress (1–4), low back pain is undoubtedly the key clinical sign to address in this population.

The VRi used in this case may alleviate pain by distracting the patient's attention from pain. The alleviation of pain is thought to be the psychological effect of immersion in the virtual space created by the VR technology (51). Another mechanism by which the VR program can reduce pain would be the creation of a relaxing atmosphere. Perception of pain is influenced by the patient's affect (52). Therefore, the positive effect induced by the psychological effects of the VR relaxation program could suppress pain perception (53).

This research should provide knowledge about the possibility of implementing VR programs in clinical environment, identifying new intervention opportunities in this group of patients.

Technical problems like device failures and technological difficulties may arise in connection with the use of VR technology. However, staff members are available to provide technical support. As possible adverse events we consider

the lack of improvement and positive evolution of the patient. We also consider as an adverse event the performance of exercise with excessive workload. Patients will be informed of the importance of warning the health professional of any incident or setback in their recovery and their right to withdraw from participation in the research at any time.

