#### Conclusions:

This study protocol is the first to examine the effect of a VR intervention added to physiotherapy in LBP and PP in a multicentre clinical setting. Efficacy and satisfaction must show if this study will add more evidence in support of the use of VR as an effective tool in pregnancy women.

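### Satisfaction with VR (USEQ) is scored only at week 4, so VR-arm women who leave the study earlier give no score and the reported satisfaction may be too favourable

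*Protocol*

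**What the plan says.** The Objectives section of the protocol sets one secondary aim: "The secondary aim is to investigate patient satisfaction with the VR intervention". The section on secondary research outcomes names the USEQ as its only instrument.

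The section on data collection describes two assessments: "Initial assessment (Pre) and final 4-week assessment (Post) will be carried out by the research team". The baseline set is FACS, RMDQ, ODI and VAS, without the USEQ. The USEQ enters only at Stage 4 (T1-Post), where the team will "compile the results of outcomes after 4 weeks including FACS, RMDQ, ODI, VAS and USEQ".

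Only the VR arm can answer it, because VR is given to that arm alone: "Subjects in the experimental group will receive an additional VR intervention". During treatment the protocol keeps a log: "Any deviations from the adherence and practice of the VRi are recorded daily, noting any adverse incidents". It does not plan a satisfaction score at that stage. The Discussion says that participants will be told of "their right to withdraw from participation in the research at any time".

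The Conclusions section then states: "Efficacy and satisfaction must show if this study will add more evidence in support of the use of VR as an effective tool".

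**The concern.** Whether a woman has a USEQ score depends on her still being in the study at week 4, and that may depend in part on how she found the headset. The Discussion itself expects device failures and technological difficulties. A woman who leaves for such a reason is the one whose rating the secondary aim most needs. She has no baseline USEQ either, so nothing stands in for the missing value. The intention-to-treat statement under Statistical analysis does not help, because it governs how collected data are analysed and cannot supply a score that was never taken.

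The Results section describes the study as a pilot that will inform whether a larger intervention is feasible. For that decision, acceptability among all women who started VR is the relevant quantity, and a mean over those present at week 4 may overstate it.

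A second, smaller matter is how the score is used. It comes from one arm and has no comparator, yet the Conclusions section names it beside efficacy as support for VR being effective.

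**Working it through.** **No figure to reproduce.** The protocol gives no USEQ mean, SD, threshold or dropout rate. The only number used from it is the arm size of 33 (Recruitment), as a head count. Whether 33 is the right size for the primary comparison is a separate question and has no bearing here.

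**What each woman contributes under the current schedule**

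| VR-arm woman | USEQ score? |
|---|---|
| Completes VR and attends week 4 | Yes |
| Stops VR but attends week 4 | Yes |
| Leaves the study before week 4 | No, at no time point |

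Only the third group is lost.

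**Size of the possible error.** Let p be the share of VR starters without a score, and D the mean satisfaction of scored women minus that of unscored women, in SD units.

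- Mean over all starters = (1 − p) × scored mean + p × unscored mean.
- Observed mean = scored mean.
- Observed minus all-starter mean = p × (scored mean − unscored mean) = p × D.

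Both p and D are assumptions:

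| p (women of 33) | D = 0 | D = 0.5 | D = 1.0 | D = 1.5 |
|---|---|---|---|---|
| 10% (3.3) | 0 | 0.05 | 0.10 | 0.15 |
| 20% (6.6) | 0 | 0.10 | 0.20 | 0.30 |
| 30% (9.9) | 0 | 0.15 | 0.30 | 0.45 |

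For scale, the standard error of a mean over 33 women is 1/√33 = 0.17 SD, and the 95% half-width is about 2.04 × 0.17 = 0.35 SD. Most of the table lies within that, but p × D is a systematic shift: it does not average out and a confidence interval does not show it.

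**A source of loss unrelated to VR.** Entry is allowed up to week 36 of gestation and the programme lasts 4 weeks, so the latest entrants reach the final assessment at 36 + 4 = 40 weeks. Some may be missing because they have delivered. For them D is plausibly near zero, which pulls the average D down, although the number scored still falls.

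**Use of the score.** The Conclusions section joins satisfaction to efficacy. The Results section makes the same kind of claim depend on benefit in the outcomes and does not mention satisfaction. The Objectives section keeps effectiveness (main objective) apart from satisfaction (secondary aim). The wording in the Conclusions section is the one that departs from the others.

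**The case against.** The best defence is that scoring at the end of the programme is a reasonable way to rate the whole programme, and that nothing shows the result to be biased. Much of this stands.

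- **Certain upward bias.** A reader might infer that the mean will be too high. The protocol does not support that: it gives no dropout rate and no reasons for leaving, the error is zero if leavers do not differ, and some losses may be due to delivery. Too favourable is the likely direction, not an established one.
- **Everyone who stops VR is unscored.** This too goes beyond the text. The right described is to withdraw from the research. A woman who gives up the headset but attends week 4 is still scored.
- **Satisfaction alone is taken as proof of effectiveness.** The Conclusions section uses it jointly with randomised outcomes, in closing prose and not as a decision rule. The lack of a comparator is inherent in a VR-specific questionnaire and is a fault only if the score is read as evidence of effect.
- **Poor tolerance is already visible.** In part: the daily log records deviations and incidents. It does not record satisfaction.
- **Little depends on the score.** No hypothesis, threshold or sample size rests on it. That limits the consequence, but it remains the only measure of the only secondary aim.

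What the defence does not answer is the missing time point. How absent scores are analysed can be left to an analysis plan. When the questionnaire is given is a matter of data collection, which this protocol fixes.

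**Conclusion.** The point holds in a limited form. VR-arm women who leave the study before week 4 have no planned USEQ score, so reported satisfaction may be too favourable as a summary for all who started VR. The excess is 0.05 to 0.45 SD if 10% to 30% are lost and leavers score 0.5 to 1.5 SD lower. Both ranges are assumptions, and the excess is nil if leavers do not differ. The randomised comparison of the primary outcomes is not affected. The sentence in the Conclusions section needs a change of wording; it does not show that the study would declare VR effective on satisfaction alone.

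**What to change.** 1. Keep the USEQ at T1-Post for women who complete the programme. Moving every score to the last VR session is not needed.
2. Add to Stages 3 and 4 that any VR-arm woman who stops VR or withdraws early is asked to complete the USEQ at that point. It must be a request only, since the Informed Consent Statement lets her leave without justification.
3. Report the number who started VR as the denominator, the number scored, and the reasons for stopping as far as the daily VR log gives them.
4. In the Conclusions section, rest effectiveness on the between-arm primary outcomes and describe satisfaction as acceptability in the VR arm.

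**Cost.** One short self-completed questionnaire for early stoppers and a few lines of text, with no change to treatment. Reported satisfaction may come out somewhat less favourable. Early scores will reflect fewer than the planned 12 sessions (3 per week for 4 weeks), so they should be identifiable as such. Women who simply do not return may still be missed, but the denominator will show how many.

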#### [Statistical analysis](#)

This research is a multicentre prospective controlled trial pre/post design. The results of the trial research will be presented as a summary of the outcome measures, together with the estimated effect size and precision. Statistical analysis will be performed according to the intention-to-treat principle. Patient characteristics will be summarized using frequencies and percentages for categorical factors, and using means and standard deviations for continuous measures in order to have as much information as possible available for exploration and analysis. The effect sizes will be calculated using the Cohen's d so that the results can be compared to other studies. The outcome measures will be compared before and after the completion of the 4 weeks program. All statistical analyses will be conducted using SPSS software. Statistical significance was set at  $p < 0.05$ .

[figure not shown]

Figure 1. Study design flow diagram: Enrollment, assessments and intervention stages

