## Background

Approximately 50% of women experience low back pain (LBP) during pregnancy; 25% continue to experience pain 1 year after delivery (1). Low-back pain (LBP) and pelvic pain (PP) are common during pregnancy and tend to increase as pregnancy advances; in some cases, the pain radiates into the buttock, leg and foot (2). Global prevalence is reported to range from 24% to 90%, in part, because there is currently no universally recognised classification system for the condition (3). For many women, pain can become so severe that it interferes with ordinary daily activities, disturbs sleep with repercussions in social and sexual life, work capacity and increased psychological stress and contributes to high levels of sick leave (4). Several factors have been identified as the possible causes of back pain in pregnancy. Mechanical strain secondary to enlarge gravid uterus is one of the causative factors which leads to compensatory lumbar lordosis (5). Besides that, separation of the abdominal muscles during pregnancy does contribute to paraspinal muscle strain. Relaxin hormone which is elevated during pregnancy is also identified as a causative factor. Hence, there will be an increase in joint laxity which may caused instability rotatory movements of sacroiliac joints (6,7).

It is estimated that over 50% of women receive little or no intervention from healthcare providers (8). European guidelines recommend that LBP and PP, are managed by providing adequate information and reassurance to patients that it is best to stay active, continue normal daily activities and work if possible, and by offering individualised exercises where appropriate. Similarly, prenatal practitioners in the United Kingdom and Nordic countries give women information about how to manage LBP, PP or both during their pregnancy and may refer them to physiotherapy for a more specific treatment programme. However, in the United States, women are taught that LBP is a normal part of pregnancy. Interventions that have been used to date to help manage the pain include exercises, frequent rest, hot and cold compresses, abdominal or pelvic support belts, massage, acupuncture, chiropractic, aromatherapy, relaxation, herbs, yoga, Reiki, paracetamol, and nonsteroidal anti-inflammatory drugs (3,4,8,9). Other forms of therapy have been studied including exercise, yoga, progressive muscle relaxation, manual therapy, acupuncture, alone or with exercises, multi-modal

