#### [Participants and eligibility criteria](#)

The trial includes pregnant women suffering from LBP, PP or the two in combination as reported symptomatically by the women or diagnosed by clinicians.

Patients must live in Sevilla or Málaga during the intervention phase, patients with history of LBP or lumbar pathology before pregnancy or have suffered LBP or PP events prior to the first contact with this research. Patients will be excluded if they have any absolute or relative contraindications such as heart disease, chronic obstructive lung disease, diabetes mellitus, incompetent cervix/cerclage, multiple gestation, risk of premature labor, preeclampsia/pregnancy-induced hypertension, thrombophlebitis, pulmonary embolism, intrauterine growth restriction, or serious blood disease, history of abortion or curettage. Also, patients are not in full cognitive capacity that allows them to use new technology tools will be excluded. Inclusion and exclusion criteria is show in Table 1.

Inclusion criteria	Exclusion criteria
Adult woman over 18 years old	Patients with LBP or PP pain prior to pregnancy.
Pregnant woman with Low Back Pain, Pelvic Pain or both conditions with symptomatic character.	Cognitive ability not suitable for the use of technological tools.
Pregnant woman between the 12th and 36th week of gestation, corresponding to the 2nd and 3rd trimester.	Patients with absolute or relative contraindications.
Pain intensity greater than 4/10 on VAS, indicating moderate-severe pain.	
Live in Sevilla or Málaga during the research period.	

Table 1. Inclusion and Exclusion criteria

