### Recruitment

In order to generate sufficient data for the development of this research a sample size of (n= 66) patients will be recruited based on previous and concluded RCT for the treatment of LBP or PP (41–43). It was calculated that a sample size of 33 women per cohort could detect a difference in outcomes of 1.0 between the VR intervention and control groups, given a SD of 1.5 and a power of 0.80.

The strategies to achieve an adequate inclusion of participants that reach the target sample size include the multidisciplinary collaboration of the gynecology, rehabilitation and physiotherapy department. The collaborators have been informed about the characteristics of the study in personal interviews and presentation. Recruitment of patients must have a socio-demographic diversity in relation to their social origin, gender, ethnicity and education adapted to the particularities of the reference population.

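### The T0 score serves only as the pre value, not as a covariate, and gestational week is unused; a between-arm model adjusted for T0 would be more efficient with data already collected.

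*Protocol*

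**What the plan says.** The Statistical analysis section labels the trial a controlled pre/post design, sets intention-to-treat, Cohen's d and a 5% significance level, and states that the outcomes are compared before and after the programme. On baseline data it says "Patient characteristics will be summarized using frequencies and percentages for categorical factors, and using means and standard deviations for continuous measures", and adds that this is meant to make information available for exploration and analysis. It names no covariate.

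The Data collection section has FACS, RMDQ, ODI and VAS completed at T0 and again at T1, so a baseline value is planned for every primary scale.

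Table 1 admits a "Pregnant woman between the 12th and 36th week of gestation, corresponding to the 2nd and 3rd trimester". The Background says that low-back and pelvic pain "tend to increase as pregnancy advances". Gestational week is not mentioned in the Statistical analysis section, and the allocation text under Intervention describes simple random numbers without stratification.

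The Recruitment section gives the design figures: "It was calculated that a sample size of 33 women per cohort could detect a difference in outcomes of 1.0", "given a SD of 1.5 and a power of 0.80".

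**The concern.** In a two-arm trial with one baseline and one follow-up measurement, there are three usual ways to compare the arms: T1 scores alone, change scores, or T1 scores adjusted for T0. The T1 comparison ignores T0. The change score subtracts T0 in full, which is too much whenever the T0-T1 correlation leaves some regression to the mean. The adjusted model estimates how much of T0 to remove, and in large samples its residual variance is never above that of the other two.

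The protocol's before/after wording points towards the change score. With only 33 women per arm, the choice can decide whether the trial reaches its planned 80% power. Gestational week is a second candidate covariate, because the protocol itself describes it as related to pain and allows a 24-week entry window.

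**Working it through.** **Inputs.** Difference 1.0, SD 1.5, power 0.80 and 33 per arm come from the Recruitment section. The 0.05 level comes from the Statistical analysis section. Assumed, because the protocol does not give them: a two-sided test, the T0-T1 correlation r (0.3, 0.5, 0.7), equal SDs at T0 and T1, and whether 1.5 is the SD of the score or of the change. Both readings of the SD are shown.

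**The plan's own figure first.** Standard error = 1.5 × √(2/33) = 0.369. Noncentrality = 1.0/0.369 = 2.71 on 64 degrees of freedom, giving power 76% (77% by the normal approximation). A two-sided 5% test needs 36 (normal) or 37 (t) per arm for 80%. So 33 per arm does not reproduce under a plain two-sample comparison with these inputs.

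**Reading A: 1.5 is the SD of the score.**
- T1 alone: SD = 1.5.
- Change score: SD = 1.5 × √(2(1 − r)) = 1.775 / 1.500 / 1.162.
- ANCOVA on T0: residual SD = 1.5 × √(1 − r²) = 1.431 / 1.299 / 1.071, with one further degree of freedom lost.

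**Reading B: 1.5 is the SD of the change.**
- Change score: SD = 1.5 at every r.
- The score SD is then 1.5/√(2(1 − r)), so the ANCOVA residual SD = 1.5 × √((1 + r)/2) = 1.209 / 1.299 / 1.383.

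**Power at 33 per arm (noncentral t):**

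| Contrast | r = 0.3 | r = 0.5 | r = 0.7 |
|---|---|---|---|
| A: T1 alone | 76% | 76% | 76% |
| A: change score | 62% | 76% | 93% |
| A: ANCOVA on T0 | 80% | 87% | 96% |
| B: change score | 76% | 76% | 76% |
| B: ANCOVA on T0 | 91% | 87% | 82% |

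ANCOVA is ahead in every column. Against the change score, the gain under reading A is about 18, 11 and 3 percentage points; under reading B it is about 15, 11 and 6. Using three covariate degrees of freedom instead of one changes these powers by less than 0.1 point.

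**Higher correlations.** For RMDQ the protocol says "Quoted test-retest correlations include 0.91 (same day), 0.88 (1 week), and 0.83 (3 weeks"; for VAS it gives 0.76 to 0.84. If such values were the T0-T1 correlation under reading A, change score against ANCOVA would be 97.1% against 98.4% at r = 0.76, and 99.6% against 99.8% at r = 0.83. Under reading B, the same two correlations give 76% against 81% and 80%.

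**Gestational week.** If entry were uniform over weeks 12 to 36 (assumed), its SD is 24/√12 = 6.93 weeks. The arm difference in mean week then has SE 6.93 × √(2/33) = 1.71 and a 95% range of about ±3.3 weeks. If week alone explained 5, 10 or 20% of outcome variance (assumed), adjusting a T1 comparison for it would give 78, 80 or 85% power under reading A, against 76% without it.

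**The case against.** **T0 is already used.** A reader might infer from the summary sentence that baseline data are used for description only and that chance imbalance in T0 goes uncorrected. The documents do not support this. T0 is one side of the before/after comparison, and a change score does remove the baseline difference between arms, though inefficiently and with over-correction. The summary sentence is ordinary descriptive text and does not rule out adjustment. This objection stands and limits the point to T0 as a covariate.

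**Gestational imbalance might seem to bias the result.** A reader might multiply an imbalance of a few weeks by a slope of pain on gestation and conclude that the treatment contrast shifts by a sizeable share of the planned 1.0. The protocol gives no slope. Under a linear slope b per week, each woman's expected natural change over 4 weeks is 4b whatever her entry week, so the imbalance cancels in a change score. It would matter there only if gestational stage altered the 4-week course, which the protocol does not say. Under randomisation, chance imbalance is also already reflected in the standard error. Week is therefore a reasonable further covariate, not a demonstrated source of error.

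**The gain depends on unstated quantities.** This is true. The quoted correlations describe test-retest reliability, not T0-T1 correlation under treatment. Entry also requires VAS above 4/10, which restricts the baseline range and may lower the VAS correlation. Neither a high nor a low value can be taken as given.

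**Covariates belong in a statistical analysis plan.** That is common, and none is shown here. A missing covariate list would not be a finding. But the protocol does state how outcomes are compared, and that stated method can be improved at no cost in data.

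**Conclusion.** The point holds as a free improvement in efficiency, not as an error that invalidates the trial. For contrasts of change scores or of T1 alone, adjustment for T0 gives higher power in every scenario examined. For r between 0.3 and 0.7, ANCOVA reaches about 80 to 96% under reading A and 82 to 91% under reading B. The change score gives 62 to 93% and 76% respectively. The benefit is about one point or less if 1.5 is the score SD and r is 0.76 to 0.83.

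The size rests on a two-sided 5% test, equal SDs at both times, an assumed correlation, and a reading of the SD that the Recruitment section leaves open. The preference for the adjusted model does not depend on which reading is right. For gestational week the support is weaker: the protocol calls it related to pain but gives no strength of relation.

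**What to change.** In the Statistical analysis section, replace the before/after wording with a statement that each primary scale is compared between arms by a linear model of the T1 score on arm, adjusted for that scale's T0 score, with gestational week at T0 and centre as further covariates. Report the adjusted arm difference with its 95% confidence interval. Fix this before outcome data are seen, so that covariates cannot be chosen on the results. In the Recruitment section, say whether 1.5 is the SD of the score or of the change.

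The cost is a sentence or two of wording and about three degrees of freedom (T0 score, week, and one for two centres). No extra visits, measurements or participants are needed: T0 scores are already scheduled, and gestational week and place of residence are checked at entry.
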